3.6.1.5 Physical Examination

All abnormal physical exam findings (pre and post-dose assessments) will be listed.

3.6.2 Immunogenicity of Tralokinumab

The incidence rate of positive serum antibodies to Tralokinumab will be reported.

Summary	Population
Summary of Subjects with Anti-Tralokinumab Antibodies	PK [×]

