3.4.2 Justification of Study Design

This study design has been reviewed and approved by the Paediatric Committee of the European Medicines Agency as part of the tralokinumab Paediatric Investigation Plan.

This is an open label study. A placebo group is not considered required for this study since the primary objective is to determine the PK of 300 mg SC tralokinumab and no formal assessment of efficacy will be made. The assessment of the safety and tolerability of tralokinumab can be made without a placebo group.

Each subject will receive a single SC dose of tralokinumab and will be followed for 57 days after investigational product administration. Based on prior data, the maximum concentration (C_{max}) of tralokinumab usually occurs between 2-9 days with a half-life of approximately 21 days after SC administration. The present sampling scheme has 7 PK samples taken within 10 days postdosing and further follow-up samples up to approximately 3 half-lives; thus providing adequate samples for the characterization of C_{max} and area under the serum concentration-time curve (AUC) parameters through a noncompartmental analysis. The

single dose and the subsequent sampling scheme will allow the estimation of PK parameters with adequate precision to achieve the objectives of the study and facilitate the future development of tralokinumab in the adolescent population.

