4.5.4 Treatment Administration

The day of dosing is considered Day 1.

The investigational product will be administered by SC injection into the tissue of the anterior thigh. Two injections (150 mg per injection) are required in order to administer tralokinumab at the required dose of 300 mg; therefore, one injection of 150 mg should be given into the anterior aspect of one thigh immediately followed by a second injection of 150 mg into the anterior aspect of the contralateral thigh.

The investigational product will be administered via a 27-gauge 1/2-inch needle. The person administering the dose will wipe the skin surface of the thigh with alcohol and allow to air dry. The skin will be pinched to isolate the SC tissue from the muscle. The needle will be inserted at a 90-degree angle approximately halfway into the SC tissue. The investigational product will be slowly injected (at least 5-second duration is recommended) into the SC tissue using gentle pressure. The area should not be massaged after injection.

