5.1.3 Day 57 ± 2 days: End of Study Visit (Visit 12)

- 1) Perform physical examination
- 2) Measure weight and height
- 3) Perform vital signs
- 4) Perform 12-lead ECG
- 5) Spirometry prebronchodilator
- 6) Collect blood for:
 - Serum chemistry

- Hematology
 - Postdose PK sample
 - Postdose IM sample
- 7) Collect urine for urinalysis and β HCG pregnancy test
 - 8) Update concomitant medication
 - 9) Assess for AEs and SAEs

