5.2.6 Immunogenicity Evaluation and Methods

Serum samples to measure the presence of ADA will be collected according to the schedule of study procedures. Instructions for sample collection, processing, storage, and shipment can be found in a separate laboratory manual provided to the sites.

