7.3.2 Secondary Endpoints

Safety and tolerability of a single-dose SC injection of tralokinumab will be assessed through the incidence of treatment-emergent AEs, and the assessment of vital signs, physical examinations, laboratory parameters, and ECG.

Immunogenicity of tralokinumab will be evaluated. The incidence rate of positive serum antibodies to tralokinumab will be reported.

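### The only post-dose ADA sample is drawn with about a fifth of peak drug expected to remain, and the SAP has no rule for negatives that residual drug might mask

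*SAP*

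**What the plan says.** Evaluating immunogenicity is a secondary objective (Protocol 2.2, SAP 3.6). Protocol 5.2.6 states that "Serum samples to measure the presence of ADA will be collected according to the schedule of study procedures". Table 5.1-1 marks that sample at two visits only. The Day 1 sample is a baseline sample taken before dosing (Protocol 5.1.2.1). The Day 57 sample is listed in Protocol 5.1.3 as "Postdose IM sample", and the same visit also includes a post-dose PK sample.

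The planned analysis is one sentence, "The incidence rate of positive serum antibodies to Tralokinumab will be reported" (SAP 3.6.2), and Protocol 7.3.2 says the same. The SAP table is for the PK population, which SAP 3.2.1 defines by having at least one detectable post-dose drug concentration.

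On pharmacokinetics, Protocol 3.4.2 says that the maximum concentration "usually occurs between 2-9 days with a half-life of approximately 21 days after SC administration" and describes "further follow-up samples up to approximately 3 half-lives".

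**The concern.** Circulating antibody drug can bind ADA and keep an assay from detecting it. How far this happens depends on the assay's drug tolerance. A negative result therefore shows absence of ADA only when the drug concentration in that sample is at or below the tolerance.

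The plan gives no tolerance, no inconclusive class, and no link between the ADA result and the drug concentration measured at the same visit. Any masked sample would fall among the non-positives. By contrast, the SAP does set rules for values below quantification in the PK data (SAP 4 and 5) and the laboratory data (SAP 3.6.1.2).

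What is at stake is the meaning of a low or zero ADA rate in adolescents, in a study that Protocol 1.5 says will enable later chronic-dosing studies in this age group.

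**Working it through.** **Inputs from the documents**
- Half-life about 21 days and time of peak 2-9 days (Protocol 3.4.2).
- "The day of dosing is considered Day 1" (Protocol 4.5.4), so Day 57 is 56 days after the dose. The ±2-day window gives 54-58 days.
- PK assay lower limit of quantification (LLOQ) 0.5 µg/mL (SAP 5). This belongs to the drug assay, not the ADA assay.
- Dose 300 mg; 20 subjects.

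**1. The plan's own figure.** 56/21 = 2.67 half-lives, which agrees with the protocol's rounded figure of about 3.

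**2. Fraction of peak left at Day 57, simple decay.** The formula is 0.5^((56 − tmax)/21).
- tmax 2 days: 0.5^(54/21) = 16.8%.
- tmax 9 days: 0.5^(47/21) = 21.2%.
- Over the visit window: 15.7% to 22.6%.

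**3. Cross-check with one compartment and first-order absorption.** Take ke = ln2/21, and solve for ka so that ln(ka/ke)/(ka − ke) = tmax. Then C(t) is proportional to exp(−ke·t) − exp(−ka·t).

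| tmax (days) | ka (per day) | C(56)/Cmax |
|---|---|---|
| 2 | 2.112 | 17.1% |
| 5.5 | 0.542 | 20.1% |
| 9 | 0.264 | 24.2% |

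Over the window the range is 16.0% to 25.9%. The two methods together give about 17-24% at the nominal visit. With an assumed half-life of 14 to 28 days, simple decay gives 7% to 31%.

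**4. Absolute concentration.** The documents give no volume of distribution and no Cmax, so this step rests on assumptions. At a 21-day half-life, C(56) is 0.160 to 0.180 times dose/(V/F).
- Assumed V/F 3-12 L: from 0.160 × 300/12 = 4.0 µg/mL to 0.180 × 300/3 = 18.0 µg/mL.
- Same V/F, assumed half-life 14-28 days: 1.6 to 27.2 µg/mL.
- To fall below 0.5 µg/mL at a 21-day half-life, V/F would have to exceed 0.160 × 300/0.5 = 96 L (tmax 2) or 0.180 × 300/0.5 = 108 L (tmax 9).

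On these assumptions, a tolerance above about 27 µg/mL leaves no negative in doubt, and one below about 1.6 µg/mL leaves all of them in doubt.

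**5. What masking would do at n = 20 (assumed rates).** With a true ADA rate of 10% and half of the positives masked, the expected reported rate is 5%. The chance of observing 0/20 rises from 0.90^20 = 12% to 0.95^20 = 36%.

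**6. Choice of denominator (assumed counts).** Take 1 positive and 19 negatives, 17 of the negatives with drug above tolerance.
- Positives over all results: 1/20 = 5%.
- Positives over positives plus evaluable negatives: 1/(1 + 2) = 33%.
- Inconclusives counted as positive: 18/20 = 90%.

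The second rate keeps positives at every drug level but drops negatives above tolerance, so it is biased upward. If all 19 negatives were above tolerance, it would be 1/1 = 100%.

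**The case against.** The strongest objection is that the harm depends on a property nobody can see here. The fraction of peak does not decide the matter; what counts is the absolute concentration against the assay's tolerance, and neither is given. This stands, and it is why the point is conditional.

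A reader might go further and infer that the reported rate is biased downward and tied to exposure. The documents do not support that. They do not say that the assay is sensitive to drug. ADA may also speed clearance, which would leave less drug in the very subjects who have ADA.

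The missing rule could also sit in a document not supplied: the laboratory manual (Protocol 5.2.6) or the statistical programming plan (SAP 1). A mark beside the population in the SAP 3.6.2 table may be a footnote whose text was lost. That is possible. However, Protocol 7.1 assigns the detail of endpoint analyses to the SAP, the manual is described as covering sample handling, and the programming plan as covering table templates and specifications. Which negatives are interpretable is part of the endpoint's definition.

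Finally, little is lost for good, and no decision rule uses the ADA rate. Individual concentrations will be listed (SAP 3.5), so results could be paired later, and Day 57 is the scheduled visit with the least residual drug after the peak. No formal testing is planned (SAP 5). Even without masking, 0/20 has an exact two-sided 95% upper limit of 1 − 0.025^(1/20) = 16.8%, so a zero rate could not establish low immunogenicity. These facts limit the consequence. They do not tell a reader of the planned table which negatives can be relied on.

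**Conclusion.** The point holds in conditional form. The documents establish a single post-dose ADA sample at 2.67 half-lives, about 17-24% of peak drug expected in it, and a bare positive rate with no class for uninterpretable negatives. If the assay's tolerance is below the Day 57 concentration, immunogenicity could be understated; if it is high enough, there is no bias from this source. The size cannot be computed from the documents.

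The 17-24% rests on the protocol's half-life and time of peak and on one-compartment kinetics. The µg/mL figures rest also on an assumed V/F. That Day 57 drug would be quantifiable depends little on that assumption at a 21-day half-life, but quantifiable drug is not the same as drug above the ADA assay's tolerance. The change is worth making because it is nearly free and settles what a low or zero rate can be taken to show.

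**What to change.** In SAP 3.6.2:
1. State the ADA assay's drug tolerance.
2. List each subject's Day 57 tralokinumab concentration beside the ADA result.
3. Report three counts: positive; negative with drug at or below tolerance; inconclusive (negative with drug above tolerance).
4. Keep the incidence as positives over all subjects with a Day 57 ADA result, and describe it as a lower bound when any result is inconclusive.
5. Give a sensitivity range: the rate with inconclusives counted as negative, then as positive.
6. Do not use positives over positives plus evaluable negatives, for the reason shown in step 6 of the working.

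Both samples are already drawn at Visit 12, so no extra visit or blood is needed. The cost is SAP wording, one extra table column, and a less definite reported rate if some negatives prove inconclusive. If the assay is sufficiently tolerant, the inconclusive count is zero and the rate is unchanged.

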3.7 Summaries to Support the Exploratory Objectives

An exploratory objective of this study is to evaluate the effect of tralokinumab on pulmonary function.

Spirometry will be performed by the investigator or qualified designee on equipment provided by a central vendor according to American Thoracic Society (ATS)/European Respiratory Society (ERS) guidelines (Miller et al, 2005). Pre-bronchodilator FEV₁ and FVC will be captured at visits 2, 3, 7, 9 and 12, post-bronchodilator FEV₁ will only be captured at screening (visit 2).

Spirometry testing must be performed in the morning between 6:00 and 11:00 AM according to the schedule of study procedures. On Day 1 (visit 3), spirometry testing will be performed before administration of tralokinumab. This will be the baseline measure.

All morning spirometry testing must be completed between 6.00 and 11.00 AM and within \pm 1 hour of the time the screening spirometry was completed. For example, if the screening spirometry is at 8:00 AM, then all spirometry testing at subsequent visits need to be completed between 7:00 and 9:00 AM.

Multiple forced expiratory efforts (at least 3 but no more than 8) will be performed for each clinic spirometry session and the 2 best efforts that meet the ATS/ERS acceptability and reproducibility criteria will be recorded. The best efforts will be based on the highest FEV₁. The maximum FEV₁ of the 2 best efforts will be used for the analysis. The percentage of predicted normal value for FEV₁ will be recorded using appropriate reference values. The highest FVC will also be reported regardless of the effort in which it occurred (even if the effort did not result in the highest FEV₁).

Reversibility is calculated as follows:

% Reversibility = (post-bronchodilator FEV_{1} - pre- bronchodilator FEV_{1}) × 100 pre-bronchodilator FEV_{1}

Spirometric parameters (FEV₁, FEV₁ % predicted, FVC, FVC % predicted and FEV1/FVC ratio at baseline and reversibility at screening) as well as the change from baseline and percent change from baseline in spirometric parameters will be summarized with descriptive statistics. A plot of mean (+/- SEM) pre-bronchodilator FEV1 over time and the mean (+/- SEM) change from baseline in pre-bronchodilator FEV1 over time will also be produced.

Summary	Population
Summary of Spirometry Results	РК
Change from Baseline in Spirometry Results	РК
Percent Change from Baseline in Spirometry Results	РК

4 Missing Data

Missing data will not be imputed unless otherwise specified in the Statistical Programming Plan. For all PK summary tables, listings and figures, serum concentrations that are below the assay's lower limit of quantitation (LLOQ) will be set to zero prior to deriving the summary statistics or plotting the concentration values. For the PK data analyses, post-dose values of "no sample" (NS), "insufficient same for analysis" (IS), or "not reported" (NR) will be omitted. Missing PK observations will not be imputed.

5 General Statistical Conventions

• For PK data, the following conventions will be used:

The Below Limit of Quantification (BLQ) observations will be changed to zero for mean concentration calculation. However, if the calculated mean is less than the assay low limit of quantification (0.5 μ g/mL), the mean value will be reported as <0.5.

- Laboratory data reported as ND (not done) will be counted as missing when calculating summary statistics.
- In general, all calculations will be performed prior to rounding.
- All percentages will be formatted as (xx.x%) with the exception of 100% which will be displayed as (100%). For 100% and percentages less than 10, a space will be included between the "(" and the first digit, for example, (6.3%) rather than (6.3%). For 0%, the percentage will be displayed as (0.0%).

- No formal testing is currently planned since all subjects receive the same treatment. However, should the cohorts be compared and P-values generated, these P-values will be rounded to three decimal digits. P-values that are less than 0.001 will be reported as "< 0.001" on the tables.
- For analyses of pre-dose laboratory data, if the time of the pre-dose laboratory collection actually occurs after dosing, the data will be excluded from analyses.
- If N = 1, then the standard deviation and/or standard error should be displayed as "NA". If N= 0, then all summary statistics (other than N) will be displayed as "NA".

6 References

GINA Report, Global Strategy for Asthma Management and Prevention, updated December 2010. Available from: http://www.ginasthma.org.

Hershey GK. IL-13 receptors and signaling pathways: an evolving web. J Allergy Clin Immunol. 2003; 111:677-90.

